| Study Manager | [REDACTED] | This document is signed electronically in the eTMF system | This document is dated electronically in the eTMF system |

INVESTIGATOR SIGNATURE PAGE

| | |
|-----------------------------|--|
| Investigator | [name] Dermatologist [name] |
| Investigational Site | EUROFINS EVIC PRODUCT TESTING ROMANIA S.R.L. [name] |

I have read this protocol and agree to conduct this study in accordance with all stipulations of the protocol and in compliance with all applicable Good Clinical Practices and regulations.

Signature of Investigator

Date

SUMMARY

| | |
|-----------------------------|--|
| Protocol Number: | MPS-17IPVSS02 |
| Protocol Title: | A Randomized, Single-Center, Partially Blinded, Evaluation of the Time-Dependent Antimicrobial Effectiveness of Swabsticks Impregnated with 2% (w/v) Chlorhexidine Gluconate in 70% (v/v) Isopropyl Alcohol in Healthy Volunteers |
| Planned Sample Size: | This study will include a minimum of 516 evaluable subjects to achieve 280 evaluable sites per anatomical location for the investigational product (IP), active control (AC), and negative control (NC) and 192 evaluable sites per anatomical location for the reference standard (RS). |
| Study Design: | This single site study is a randomized, controlled, partially-blinded design enrolling a minimum of 516 healthy volunteers, where each subject will receive two of the planned study products on the product application sites of the abdomen and/or groin. |
| Study Methodology: | ASTM Standard Test Method E1173-15 |
| Study Population: | 
Healthy male and female volunteers, 18 years of age or older.
 
Screening Day bacterial count requirements of at least 3.20 log₁₀/cm² on the abdomen and 5.50 log₁₀/cm², on the groin.
 
Product Application Day baseline bacterial count requirements are in the range of 3.20 to 6.00 log₁₀/cm², inclusive, on the abdomen or 5.50 to 7.50 log₁₀/cm², inclusive, on the groin.
 |

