6.3.3 Bacterial Enumeration Methods

Following sample collection, 10-fold serial dilutions (1 mL sample + 9 mL PBW) will be prepared using PBW. One-mL aliquots of appropriate dilutions will be pour-plated in triplicate using trypticase soy agar containing neutralizers (TSA+N). Samples must be plated within 30 minutes of collection.

Serial dilutions of collected baseline screening samples as follows:

- for groin sites: 1 serial dilution (10^{-3})
- for abdomen sites: 1 serial dilution (10^{-1})

Serial dilutions of collected treatment day (D0) samples as follows:

for groin sites

- Baseline: 3 serial dilutions (10^{-3} , 10^{-4} and 10^{-5})
- 30 seconds: 6 serial dilutions (10^0 , 10^{-1} , 10^{-2} , 10^{-3} , 10^{-4} and 10^{-5})
- 10 minutes: 6 serial dilutions (10^0 , 10^{-1} , 10^{-2} , 10^{-3} , 10^{-4} and 10^{-5})
- 6 hours: 6 serial dilutions (10^0 , 10^{-1} , 10^{-2} , 10^{-3} , 10^{-4} and 10^{-5})

for abdomen sites

- Baseline: 3 serial dilutions (10^{-1} , 10^{-2} and 10^{-3})
- 30 seconds: 4 serial dilutions (10^0 , 10^{-1} , 10^{-2} and 10^{-3})
- 10 minutes: 4 serial dilutions (10^0 , 10^{-1} , 10^{-2} and 10^{-3})
- 6 hours: 4 serial dilutions (10^0 , 10^{-1} , 10^{-2} and 10^{-3})

After 72 ± 4 hours of aerobic incubation at $30 \pm 2^\circ\text{C}$, colonies will be counted and viable cells in the original sample will be calculated according to Standard Operating Procedures (SOPs). After incubation, plates may be refrigerated up to 48 hours prior to counting.

Raw colony counts from each dilution will be recorded on the appropriate CRFs for each subject. The average number of microorganisms recovered will be calculated using the formula to convert the bacterial counts into \log_{10} CFU/cm² of skin:

$$R = \log_{10} \left[\frac{F \left(\frac{\sum_{i=1}^3 c_i}{n} \right) D}{A} \right]$$

Where: R = the average CFU count in \log_{10} scale per cm² of skin.

F = total mL of sampling solution (SS) added to the sampling cylinder (6 mL);

$\frac{\sum_{i=1}^3 c_i}{n}$ = average of the triplicate colony counts used for each sample collected

D = Dilution factor of the plates counted. One of 10^0 , 10^1 , 10^2 , 10^3 , 10^4 , or 10^5 .

A = Inside area of the sampling cylinder (3.80cm²)

The average CFU/mL, CFU/cm², and \log_{10} CFU/cm² will be calculated for samples from each product application site in the same manner.

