13.3 Study Populations

The full intent-to-treat (ITT) data set (all randomized subjects that received study product) will be used for the safety analysis.

A modified intent-to-treat (mITT) data set will be used for efficacy analyses. Inclusion for the mITT data set is evaluated for each anatomical site (left and right for the groin and abdomen). For each anatomical site, if the product application day baseline bacterial count is in the range of 3.20 to 6.00 \log_{10}/cm^2 , inclusive, on the abdomen or 5.50 to 7.50 \log_{10}/cm^2 , inclusive, on the groin, then the data from that anatomical site are included in the mITT data set.

Analyses conducted on the mITT data set will also be conducted on the Per Protocol data set as supportive analyses when Per Protocol data are different from mITT data.

The Per-Protocol data set will include evaluable product application sites from the mITT data set that adhere to defined assessments and procedures in the protocol central to patient enrollment, safety, rights or wellbeing, as well as the completeness, accuracy and reliability of study data. Additional details on qualification for the PP data set are outlined in the SAP.

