6.1 Derived Variables

6.1.1 Log₁₀ CFU/cm² of skin

Raw colony counts from each dilution will be recorded on the appropriate eCRFs for each subject. The average number of microorganisms recovered will be calculated using the formula below to convert the bacterial counts into log₁₀ CFU/cm² of skin:

$$R = \log_{10} \left[\frac{F \left(\frac{\sum_{i=1}^3 C_i}{n} \right) D}{A} \right] \quad (1)$$

Where:

R = the average CFU count in log₁₀ scale per cm² of skin.

F = Total number of mL of stripping fluid added to the sampling cylinder (6 mL). Note: If sample solution is lost during the procedure for a certain time point, the F value for that time point will change from 6 mL to the “Volume Remaining (mL)” recorded in the Core Lab Procedure Overview eCRFs.

$\frac{\sum_{i=1}^3 C_i}{n}$ = average of the triplicate colony counts used for each sample collected (n = 3).

D = Dilution factor of the plates counted. One of 10⁰, 10¹, 10², 10³, 10⁴, or 10⁵.

A = Inside area of the sampling cylinder in cm² (3.80 cm²).

The average CFU/mL, CFU/cm², and log₁₀ CFU/cm² will be calculated for samples from each product application site in the same manner.

In order to avoid potential calculation problems due to taking the logarithm of zero, values of less than 1 CFU/cm² will be treated as 1 CFU/cm², such that the log₁₀ transformation is not less than zero.

If colonies on one of the plates are uncountable, the average count from the remaining plates will be used. If colonies on two of the plates are uncountable, the count from the remaining plate will be used. If colonies on three plates are all uncountable, the average count will be missing.

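### Abdomen plating stops at 10^-3, where the 6.00 log10 mITT limit means 633 colonies per plate. If the unstated counting limit is lower, in-window baselines are recorded as missing.

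*SAP*

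**What the plan says.** Protocol 6.3.3 fixes the treatment-day dilutions. "One-mL aliquots of appropriate dilutions will be pour-plated in triplicate". Abdomen baselines are plated at 10^-1, 10^-2 and 10^-3, and abdomen post-application samples at 10^0 to 10^-3. Groin baselines are plated at 10^-3, 10^-4 and 10^-5. Colony counting and calculation follow SOPs that the documents do not include.

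Protocol 13.3 admits an abdomen site to the mITT set if its "product application day baseline bacterial count is in the range of 3.20 to 6.00" log10/cm², both ends included. For the groin the window is 5.50 to 7.50. SAP 5.2 and Table 1 repeat the rule and apply it site by site.

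SAP 6.1.1 uses the remaining plates when one or two are uncountable. For the whole triplicate it says "If colonies on three plates are all uncountable, the average count will be missing". Uncountable is not defined. The same section has a rule for the low end (values under 1 CFU/cm² become 1) but none for the high end.

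**The concern.** The dilution series should let every count inside the inclusion window be read. The groin series does. The abdomen series fits at its lower end but needs a much denser plate at its upper end.

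A sample whose plates are overgrown at the highest dilution is known to be high. Calling it missing discards that knowledge. For a baseline, the site can then not be shown to meet the mITT rule, and a true value of 5.9 looks the same as a true value of 6.5.

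Nothing earlier in the study catches this. Screening sets only a minimum count (Protocol 4.1), so high-count volunteers proceed. Product is applied once the baseline samples are collected (Protocol 6.1.6.3), while the plates incubate for 72 ± 4 hours (6.3.3). A lost site is found only after the volunteer has been treated.

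**Working it through.** **Plan's own figure.** The documents give no colonies-per-plate figure. Their stated power for all six FDA objectives (over 95% at 280 sites per arm) does reproduce. With SD 1.05 (abdomen) and 1.2 (groin), the distances to the criteria are 0.5 − 0.06 = 0.44 and 1.58 − 1.2 = 0.38 for the abdomen, and 0.5 − 0.10 = 0.40 and 2.31 − 1.2 = 1.11 for the groin. Powers are 0.9986, 0.9899, 0.9764 and 1.000. The abdomen pair counts twice (10 minutes and 30 seconds), so 0.9986² × 0.9899² × 0.9764 × 1.000 = 0.954. The present point does not depend on this figure.

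**Inputs.** F = 6 mL, A = 3.80 cm² and R = log10(F × mean count × D / A) (Protocol 6.3.3, SAP 6.1.1); the dilutions and windows are as above.

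**Step 1: colonies per plate at each window limit.** Inverting the formula, mean count = 10^R × A / (F × D).

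| Limit | D | Calculation | Colonies per plate |
|---|---|---|---|
| Abdomen 3.20 | 10^1 | 10^3.20 × 3.80 / 60 | 100 |
| Abdomen 6.00 | 10^3 | 10^6 × 3.80 / 6,000 | 633 |
| Groin 5.50 | 10^3 | 10^5.50 × 3.80 / 6,000 | 200 |
| Groin 7.50 | 10^5 | 10^7.50 × 3.80 / 600,000 | 200 |

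Only the abdomen upper limit is out of line.

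**Step 2: highest readable abdomen value at 10^-3.** The counting limit c is an assumption, because the documents give none. Ceiling = log10(6 × c × 1,000 / 3.80).

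| Assumed c | Ceiling (log10) | Gap to 6.00 |
|---|---|---|
| 250 | 5.60 | 0.40 |
| 300 | 5.68 | 0.32 |
| 400 | 5.80 | 0.20 |
| 500 | 5.90 | 0.10 |
| 600 | 5.98 | 0.02 |
| 634 or more | 6.00 or more | none |

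**Step 3: share of in-window abdomen sites above the ceiling.** The baseline distribution is also not given. Assume a normal distribution truncated to 3.20-6.00; share = [Φ(6.00) − Φ(ceiling)] / [Φ(6.00) − Φ(3.20)], with Φ the assumed baseline's distribution function.

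| Baseline mean, SD | c = 250 | c = 300 | c = 500 | c = 600 |
|---|---|---|---|---|
| 4.0, 0.5 | 0.1% | 0.0% | 0.0% | 0.0% |
| 4.4, 0.7 | 3.5% | 2.4% | 0.5% | 0.1% |
| 4.8, 0.9 | 11.1% | 8.5% | 2.3% | 0.5% |

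Per 280 in-window sites, the middle row at 250-300 colonies is about 7 to 10 sites, and the largest entry is about 31. A more extreme baseline (mean 5.0, SD 1.0) would give 14.5% at 250 colonies.

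**Step 4: effect of one more dilution.** At D = 10^4, a value of 6.00 needs 10^6 × 3.80 / 60,000 = 63 colonies. With c = 250-300 the ceiling rises to 6.60-6.68, above the window.

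**The case against.** The strongest reply is that the loss is conditional. A reader might infer that eligible high-count sites do drop out of the mITT set. The documents do not support that: they give no counting limit, and if the SOP allows about 634 colonies or more per plate there is no gap. The 11% figure also combines a low counting limit with a high and widely spread baseline. Protocol Appendix 6 puts normal skin flora at roughly 10^2 to 10^5 CFU/cm², which suggests few abdomen counts near 6.00. That is only indicative, since the groin window lies above that range.

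A reader might also infer biased treatment contrasts. The documents point the other way. Baseline is sampled before application, so its loss should not depend on the product. Protocol 3.3.1 randomizes further subjects to make up baseline failures, so the 280 and 192 targets and the power hold. An unreadable post-application count leaves the site in the mITT set with a missing response, not imputed in the main analyses (SAP 6.4). That would fall mainly on saline sites, lower the saline mean and shrink NC − IP, against the sponsor. Predictive mean matching cannot restore values above the ceiling, but on the plan's effect sizes few post-application counts should reach it.

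Uncountable need not mean overgrown, and SAP Table 4 already lists undosed or contaminated plates as a separate exclusion. This stands, but it leaves the term undefined and gives overgrown plates no rule of their own.

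The work is not trivial either: plating must be done within 30 minutes of collection. That is a reason to confine the extra dilution to baseline samples.

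**Conclusion.** The concern holds in conditional form. It is established that abdomen plating ends at 10^-3, that 6.00 log10 there means 633 colonies per plate, and that an all-uncountable triplicate becomes missing whatever the reason. Whether sites are lost depends on a counting limit the documents do not state; the loss occurs only below about 633.

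Under the assumptions shown, the loss is 0 to about 11% of in-window abdomen sites, and about 2-4% at 250-300 colonies with a mid-range baseline. What is at stake is an mITT window that may not be applied as written at its upper end, and volunteers exposed to replace sites whose baselines could not be read. Neither the power nor the validity of the comparisons is threatened to any important degree. It merits correction because the remedy is specific and cheap.

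**What to change.** 1. In Protocol 6.3.3, add 10^-4 to the abdomen Product Application Day baseline series. The cost is three plates per sample: 516 subjects × 2 abdomen sites × 3 = 3,096 plates, plus those for any additional subjects. Extending this to all four time points would take 12,384 plates and is not needed.

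2. In SAP 6.1.1, state the counting limit per plate and separate samples too numerous to count at the highest dilution from contaminated or lost plates. Class a too-numerous baseline as above the window. Set a too-numerous post-application count to the ceiling value and flag it as right-censored. Keep missing for everything else. This costs a few sentences.

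3. If no dilution is added, state the measurable upper limit in place of 6.00 and treat too-numerous baselines as out of window. Do not set them equal to that limit: the window is inclusive, so sites truly above 6.00 would be admitted.

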6.1.2 Log Reduction

Log₁₀ CFU/cm² reductions from baseline will be calculated separately for each subject, each of the four sites (left and right for the abdomen and groin), and each post-product application sampling time by taking the baseline log₁₀ CFU/cm² values and then subtracting the log₁₀ CFU/cm² values for the samples taken after baseline. The mean log₁₀ CFU/cm² changes from baseline will be calculated separately for each product, at each anatomical site (abdomen and groin), and at each post-product application sampling time point (30 seconds, 10 minutes and 6 hours).

6.1.3 Responder Rate

To evaluate the persistent antimicrobial properties of a single Swabstick impregnated with 2% (w/v) chlorhexidine gluconate in 70% (v/v) isopropyl alcohol, log₁₀ bacterial counts at 6 hours post-product application for each product application site will be converted to a binary (yes or no) success measure with success defined as having skin flora counts that are less than or equal to the baseline skin flora counts.

6.1.4 Product Weight

The weight (grams) of product solutions applied to an anatomical area will be estimated as:

Product weight prior to product application (g) - product weight post-product application (g)

6.2 Analysis Methods

6.2.1 HC Analysis

6.2.1.1 Summary Statistics

The following descriptive statistics for \log_{10} CFU/cm² at each time point (baseline, 30 seconds, 10 minutes and 6 hours) and \log_{10} CFU/cm² reductions at each post application sampling time point (30 seconds, 10 minutes and 6 hours) will be computed for the IP and RS, grouped by anatomical site: mean, median, standard deviation, minimum, maximum, and count (cf. Tables [A.2.1](#) and [A.2.2](#)).

6.2.1.2 Primary Analysis

The 95% confidence intervals (two-sided) will be calculated for the average log reductions for the IP and RS at each post application sampling time point on each anatomical area using one-sample t-test (two-sided). The 95% confidence lower bound for mean log reduction at 30 seconds and 6 hours will be compared to the acceptance criteria (cf. Table [A.2.4](#)).

- If the lower limit of the 95% confidence interval (two-sided) of mean log reduction at 30 seconds is greater than or equal to 2 on the abdomen, acceptance criteria are met on the abdomen at 30 seconds.
- If the lower limit of the 95% confidence interval (two-sided) of mean log reduction at 30 seconds is greater than or equal to 3 on the groin, acceptance criteria are met on the groin at 30 seconds.
- If the lower limit of the 95% confidence interval (two-sided) of mean log reduction at 6 hours is greater than or equal to 2 on the abdomen, acceptance criteria are met on the abdomen at 6 hours.
- If the lower limit of the 95% confidence interval (two-sided) of mean log reduction at 6 hours is greater than or equal to 3 on the groin, acceptance criteria are met on the groin at 6 hours.

The RS will be also compared to the acceptance criteria applied to the IP.

6.2.1.3 Exploratory Analysis

The same analysis as described in Section [6.2.1.2](#) will be performed for log reduction at the 10 minute time point on each anatomical area for the IP and RS using one-sample t-test (two-sided) (cf. Table [A.2.5](#)).

\log_{10} CFU/cm² reductions at 30 seconds, 10 minutes, and 6 hours on the abdomen and the groin for the IP will be compared to the RS using two-sample t-test (two-sided). Difference in log reduction along with 95% confidence interval (CI) at each post application sampling time point will be compared to zero. If 95% CI contains zero, the conclusion is no significant difference in log reduction between IP and RS. If 95% CI does not contain zero, the conclusion is significant difference in log reduction exists and the direction of the difference will be indicated (cf. Table [A.2.6](#)).

A graph for the log reduction at each post application sampling time point with 95% confidence interval will be provided (cf. Figure C.1.1 created based on the simulated data).

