6.1.6.1 Preparation of abdominal product application area

A skin irritation assessment will be performed by the Investigator or designee trained by the Investigator, using the Skin Irritation Rating Scale (Table 6). If an irritation score of 1 or greater is assigned for any individual skin condition at the Product Application Day baseline, the subject will be excluded from the product application phase of the study for the abdomen.

The product application site within the abdominal region (abdominal product application area) is defined as the area to the right and left sides of the abdomen, adjacent to the umbilicus that appear to be similar in condition and above the groin (APPENDIX 1). Using a 2.5" x 2.5" (6.4 cm x 6.4 cm) sterile template, the corners of each abdominal product application area will be marked directly on the skin using a non-toxic skin marker. Four sampling sites will

be numbered within each abdominal product application area, on each side of the abdominal region. The positioning and numbering of the abdominal sampling sites are standard for all subjects. Sampling sites on the contra-lateral side of the abdomen will be numbered in a mirror-image orientation. The four sampling sites within each abdominal product application area represent one baseline (pre-application) site and three post-application sample sites (30seconds, 10-minutes, and 6-hours).

After abdominal product application areas are marked and sample sites numbered, baseline samples will be collected from the appropriate site per the randomization schedule in each product application area using the scrub cup technique (see Section 6.3.1.1 Microbial Sample Collection/ Scrub Cup Technique).

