13.5.2 HC Exploratory Analyses

1. The following descriptive statistics for \log_{10} CFU/cm² reductions will be computed for the IP and RS, grouped by anatomical site and each post application sampling for the 10 minute time point: mean, median, standard deviation, minimum, maximum, and count. The 95% confidence intervals (two-sided) will be calculated for the observed log reductions for the IP and RS at the 10 minute time point on each anatomical area using one-sample t-test (two-sided).
2. \log_{10} CFU/cm² reductions at 30 seconds, 10 minutes, and 6 hours on the abdomen and the groin for the IP will be compared to the RS using two-sample t-test (two sided).

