2.2.2.2 Exploratory Objective

- To evaluate the \log_{10} CFU/cm² reductions from baseline for the IP and RS at each anatomical site, abdomen and groin, at 10 minutes post-product application.
- To determine if the 30-second, 10 minutes and 6 hour \log_{10} CFU/cm² reductions on the abdomen and groin for the IP are not statistically worse than those for 60% v/v 1-propanol post-product application.

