3.2 FDA Analysis

To evaluate the primary and secondary objectives for the US FDA analysis a sample size of 280 evaluable sites per study product arm (IP, AC or NC) per body site can achieve > 95% power to demonstrate the non-inferiority of the Investigational Product (IP) as compared to the Active Control (AC) and the superiority of the IP as compared to the negative control (NC) in antimicrobial effect at 30-second (abdomen only) and 10-minute (abdomen and groin) post-product application time point for all six objectives, with the following assumptions in Table 3.

Table 3: Parameters Used in Sample Size Calculations For FDA Analysis

Two-sided test Type I error (α) : 0.05		
Average Treatment Effect	Abdomen (\log_{10})	Groin (\log_{10})
IP - AC	0.06	0.10
NC - IP	1.58	2.31
Standard deviation for each product on Abdomen: 1.05 \log_{10}		
Standard deviation for each product on Groin: 1.2 \log_{10}		

The overall power to pass both HC analysis and FDA analysis acceptance criteria is > 90%.

4 Intended Statistical Software

The analyses will be performed using R version 3.6.0 (2019-04-26) [2] or higher. R libraries and versions that are used for analyses will be listed.

5 Data

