6.2.2.2 Primary Analysis

A linear regression model for each body site (abdomen or groin) will be used for primary analysis of efficacy at 10 minutes. In the model, the response is the post-product application bacterial counts at 10 minutes and predictors are the study products (IP, AC or NC) as a fixed effect and the pre-product application bacterial loads as a covariate. The average treatment effect (ATE) corrected for pre-product application bacterial loads will be estimated from the model and compared to both non-inferiority and superiority criteria (cf. Table A.3.5).

For assessment of the four primary objectives (i.e., immediate activity at 10 minutes post application on the abdomen and groin for non-inferiority and superiority):

- A non-inferiority criterion with a 0.5 \log_{10} margin will be implemented for ATE of the IP compared to the AC (i.e., if the upper two-sided 95% confidence bound of the post-product application bacterial load corrected for pre-product application bacterial load of the IP-AC is less than 0.5 \log_{10} , the non-inferiority criterion is met).
- A 1.2 \log_{10} superiority criterion will be implemented for the ATE of the IP compared to the NC (i.e., if the lower two-sided 95% confidence bound of the post-product application bacterial load corrected for pre-product application bacterial load of the NC-IP is greater than 1.2 \log_{10} , the superiority criterion is met).

A graph showing the ATE with 95% confidence intervals for post-product log CFU at 10 minutes correcting for pre-product application will be provided for each contrast (cf. Figure C.2.1 created based on the simulated data).

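### The exploratory comparison of IP with 1-propanol has no baseline covariate, which probably costs it a little precision

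*SAP*

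**What the plan says.** SAP 6.2.1.3 compares IP with RS at three time points and two body sites: log reductions "on the abdomen and the groin for the IP will be compared to the RS using two-sample t-test (two-sided"). Protocol 13.5.2 has the same test ("will be compared to the RS using two-sample t-test (two sided"), and so does the protocol summary. The variable analysed is a change score. Under SAP 6.1.2, "reductions from baseline will be calculated separately for each subject, each of the four sites (left and right for the abdomen and groin"), as the baseline value minus the later value.

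The decision rule has no margin: "If 95% CI contains zero, the conclusion is no significant difference in log reduction between IP and RS". It serves the exploratory objective (SAP 2.2.2.2) that the IP reductions "are not statistically worse than those for 60% v/v 1-propanol".

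Baseline is available at every site. For the abdomen, Protocol 6.1.6.1 says that "baseline samples will be collected from the appropriate site per the randomization schedule in each product application area using the scrub cup technique"; 6.1.6.2 does the same for the groin. A site enters the mITT set only with a baseline in the window (SAP 5.2 and Table 1). For IP versus AC and NC, the same SAP uses that baseline as a covariate: "predictors are the study products (IP, AC or NC) as a fixed effect and the pre-product application bacterial loads as a covariate" (6.2.2.2). No such analysis is planned for IP versus RS, even as support.

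**The concern.** A t-test on change scores is fully efficient only if post-application counts rise one for one with baseline. If they rise less steeply, subtracting the whole baseline adds baseline variation to the outcome. It also leaves part of any chance baseline difference between the products in the estimate, with the sign reversed.

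Two features of the plan make a slope below 1 likely.

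- **Floor.** Counts below 1 CFU/cm² are set to 1 (Protocol 6.3.3, SAP 6.1.1), so a log reduction cannot exceed its own baseline. The abdomen window opens at 3.20, but the planned mean reductions there are 3.47 and 3.43. A site entering at 3.20 cannot reach the planned mean.
- **Different skin.** Each application site is divided into four areas, each sampled once (Protocol 3.3.1), so baseline and post counts never come from the same area.

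At stake is the width of six exploratory intervals. Width matters somewhat because an interval that contains zero is reported as no significant difference.

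**Working it through.** **The plan's own figures.** No power, SD or interval width is stated for IP versus RS. The SDs used below come from the HC sample size (Protocol 13.1, SAP 3.1), so I first checked that they give the stated HC power. One-sample t-test, two-sided 0.05, n = 192, noncentrality = (mean - criterion) / (SD / √192):

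- Groin 30 s: (3.38 - 3) / (1.43 / 13.856) = 3.68, power 0.956.
- Groin 6 h: (3.50 - 3) / (1.24 / 13.856) = 5.59, power 0.9998.
- Abdomen 30 s and 6 h: power 1.000 each.

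The product is 0.956, which agrees with the stated figure of more than 95%.

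**Width of the planned interval.** There are 280 IP and 192 RS sites. I take the RS SD equal to the IP SD and the groups as independent (both assumptions).

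Half-width = t(0.975, 470) × SD × √(1/280 + 1/192) = 1.965 × 0.0937 × SD = 0.1841 × SD.

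- 30 s: abdomen 0.1841 × 1.14 = 0.210; groin 0.1841 × 1.43 = 0.263.
- 6 h: abdomen 0.1841 × 1.22 = 0.225; groin 0.1841 × 1.24 = 0.228.
- 10 min: the documents give no SD for the log reduction.

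**Effect of a baseline covariate.** Let b be the slope of post count on baseline and s the baseline SD. Then change-score variance = residual variance + (1 - b)² s², and the adjusted comparison keeps only the residual variance. So

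adjusted / planned width = √(SD² - (1 - b)² s²) / SD.

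The documents give neither b nor s. Assumed: s from 0.3 to 0.6, b from 0 to 0.5. Reduction in width:

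| | b = 0, s = 0.3 | b = 0, s = 0.6 | b = 0.5, s = 0.3 | b = 0.5, s = 0.6 | b = 1 |
|---|---|---|---|---|---|
| Abdomen 30 s (SD 1.14) | 3.5% | 15.0% | 0.9% | 3.5% | 0 |
| Groin 30 s (SD 1.43) | 2.2% | 9.2% | 0.6% | 2.2% | 0 |
| Abdomen 6 h (SD 1.22) | 3.1% | 12.9% | 0.8% | 3.1% | 0 |
| Groin 6 h (SD 1.24) | 3.0% | 12.5% | 0.7% | 3.0% | 0 |

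Example, abdomen 30 s, b = 0, s = 0.6: √(1.2996 - 0.36) / 1.14 = 0.969 / 1.14 = 0.850, so the half-width falls from 0.210 to 0.178. On the groin at 30 s the largest change in the table is from 0.263 to 0.239.

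**Simulation.** This applied the baseline windows, the floor and 64 subjects receiving both products, with baseline SD 0.5 and residual SD 1.0 (abdomen) or 1.2 (groin). The adjusted-to-planned ratio was 0.89 at slope 0 and 0.96 at slope 0.5 on the abdomen, 0.94 and 0.98 on the groin, and 1.00 at slope 1 on both. The adjusted interval was narrower in 98-100% of runs at slope 0 or 0.5. Correlation within the 64 subjects hardly moved the ratios.

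**Chance imbalance.** With s = 0.5 (assumed), the baseline difference between IP and RS has standard error 0.5 × 0.0937 = 0.047, so differences up to 1.96 × 0.047 = 0.09 log10 are ordinary. The change score leaves a share (1 - b) of that in the estimate.

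**The case against.** The planned test is a valid, unbiased randomised comparison, and log reduction is the HC endpoint itself. The change score already uses baseline, so a reader who infers that baseline is ignored goes too far: only the slope is fixed. The comparison is exploratory, with no acceptance criterion and no power statement, and SAP 6.4 excludes exploratory objectives from sensitivity analysis. The protocol summary plans an ANOVA of baseline values by product, though it attaches no consequence to a difference. All of this stands. It limits the point to efficiency but does not remove it.

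A reader might also infer a 16% gain on the groin by setting the FDA planning SD of 1.2 against 1.43 (1.2 / 1.43 = 0.839). The documents do not support that:

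- It needs (1 - b) × s = √(1.43² - 1.2²) = 0.78. A uniform spread over the 5.50-7.50 window gives only 2 / √12 = 0.58. Even at slope 0, that spread yields √(2.0449 - 0.3333) / 1.43 = 0.915, about 8.5%.
- The 1.2 was planned for 10 minutes on the groin, while 1.43 is for 30 seconds. Against the 6-hour SD of 1.24, the same 1.2 would give 3%.
- Neither document says that the FDA SDs are baseline-adjusted. SAP 3.2 has only "Standard deviation for each product on Abdomen: 1.05" and the matching groin line, and Protocol 13.1 attaches the SDs to the treatment effect. The 8% that 1.05 against 1.14 would suggest for the abdomen rests on the same unstated assumption.

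Finally, the half-widths treat the groups as independent. Four blocks of 16 put 64 subjects on both IP and RS (Protocol 3.3.1). The absolute widths are therefore approximate, and neither the t-test nor the covariate model deals with the pairing.

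**Conclusion.** The point holds as a low-severity gain in efficiency. With 472 sites the adjusted interval is narrower in expectation unless the slope is 1, and at slope 1 essentially nothing is lost. At 30 seconds the gain is about 1-15% on the abdomen and 1-9% on the groin. These ranges assume a baseline SD of 0.3-0.6, a slope of 0-0.5, equal SDs for IP and RS, and independent groups. They are not bounds, because the documents do not fix the baseline SD or the slope; the 0.6 end already slightly exceeds a uniform spread on the groin.

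No HC or FDA success criterion depends on this comparison. A reader might infer that adjustment would make the conclusion about 1-propanol sound. It would not: an interval that contains zero still does not show that IP is no worse, because no margin is set, and a slightly narrower interval does not supply one.

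**What to change.** In SAP 6.2.1.3, at each body site and time point, regress log reduction on product (IP, RS) and baseline log10 count. Report the adjusted IP-RS difference with its 95% CI in Table A.2.6. The t-test may stay as a supportive analysis. With log reduction as the response, the product coefficient and its standard error match those from a model of the form in SAP 6.2.2.2 apart from sign, so the table layout and direction do not change.

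The cost is one degree of freedom and no data: every mITT site has a baseline, so none is lost. The adjusted difference will not exactly equal the difference of the raw means in Tables A.2.2, A.2.4 and A.2.5, and a footnote should say so. Protocol 13.5.2 and the protocol summary need matching wording, which goes beyond the administrative changes described in Protocol 15.4. The missing margin and the 64 subjects who receive both products are separate matters that this change leaves open.
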